## STUDY PROCEDURES

**Overview of protocol:** The protocol consists of screenings followed by 3 experimental Phases. Individuals diagnosed with PTSD who report frequent TRNs will be recruited from the MGH-Red Sox Foundation's Home Base program, the Boston VA Medical Center, local hospital trauma clinics, and from the community. Interested individuals will first complete a telephone screening followed by a series of structured clinical interviews using a Zoom Healthcare Secure Room to diagnose PTSD and comorbid psychiatric disorders, confirm initial inclusion criteria, rule out exclusion criteria and create an audio-recorded account of their index trauma. Participants passing screenings will then proceed to Phase 1 and complete 2 weeks of at-home sleep and nightmare diaries and time-stamped audio-recorded reports of dream content upon awakening from any nightmare. They will also wear a wrist actigraph throughout this period, complete two to four nights of ambulatory PSG, and complete on-line guestionnaires. Nightmare data will be examined for frequency and thematic similarity of nightmares to a participant's reported index trauma. Those reporting at least 4 such nightmares with at least one that is clearly related to the index trauma and sufficiently detailed for script creation will be invited to participate in Phase 2. Phase 2 participants will undergo a structural MRI scan and will then be scheduled to undergo MRI-guided positioning of fNIRS sources and optodes using the BrainSight2 System. Phase 3. Participants' nightmare and index trauma reports will be audio-recorded for use as scripts during SDI. The participant will then undergo two SDI sessions on a single day, one with a nightmare script and one with an index-trauma script, during which they will wear the NINscan. Sessions will be separated by 1 hour and counterbalanced across participants for script order.

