**Phase 2:** Participants will undergo a structural T1 MPRAGE MRI scan. This will be used along with the BrainSight Frameless Stereotactic System (Rogue Research, Inc., Montreal, CN) to localize fNIRS optodes at 8 bilateral regions of interest (ROIs) (4 per hemisphere) including the frontopolar cortex (BA 10), as well as superior (BA 9), middle (BA 46) and inferior (BA 47) frontal gyri.

**Phase 3:** When we capture a suitable nightmare from a participant, the recorded nightmare report will be transcribed and audio-recorded by an investigator as a TRN script following our standard procedures. Participants will then come to the laboratory and complete 2 SDI sessions with NINscan monitoring, one of which will use the script derived from the TRN and the other the script derived from the index trauma. Presentation order of the scripts derived from the TRN and from the index trauma will be counterbalanced across participants. Because PTSD symptomatology and extinction memory may vary with the menstrual cycle, female participants not on oral contraceptives will undergo SDI during the early follicular phase of their cycle.

**Script Driven Imagery**: Adapting standardized SDI protocols, scripts will be created from audio-recorded accounts of the index trauma about which a participant's TRNs represent a re-experiencing. The audio-recorded report and list of bodily sensations experienced from an awakening during Phase 1 will provide material for the nightmare script. Account of a second personalized stressful event unrelated to the index traumatic event will be similarly recorded as well as one recording each of a recalled positive and emotionally neutral experience. These accounts will be transcribed and the subject will clarify and expand on details as necessary. Scripts approximately 30 sec in duration will then be composed and recorded by experienced staff, portraying each experience in the second person, present tense. Six 30-sec standard generic scripts of both neutral and emotional situations (2 each of neutral, fearful and positive

experiences) will also be recorded. Script recordings will be played to participants through headphones as they vividly imagine each event and physiological data are continuously sampled.

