**Actigraphy and sleep diary:** The waterproof Actiwatch 2 (Philips Respironics, Bend, OR) is worn on the non-dominant wrist 24h/day and counts arm movements in 1-min epochs. Participants press an event marker when beginning to attempt sleep and when waking for the day. Epochs are scored as sleep or wake using a standardized algorithm. The EMSQ queries daytime activities and the time one begins attempting sleep (evening), and wake time, subjective sleep latency, total sleep time, and number of awakenings (morning).

**Self-report assessments:** A secure online MGH system will obtain the: 1.) Pittsburgh Sleep Quality Index  with PTSD addendum; 2.) Insomnia Severity Index; 3.) Morningness-Eveningness questionnaire; 4.) Spielberger State-Trait Anxiety Inventory; and 5.) Inventory of Depressive Symptomatology.

**Outcome and predictor variables:** For Hypothesis 2, outcomes will be "difference scores" between biosignals from the 30-s trauma-related epoch of the nightmare and index-trauma SDI and their baseline epochs (30 s of silence preceding the respective script). For fNIRS, the quantities used to compute difference scores will be  $O_2$ Hb minus HHb concentrations (HbD)

at each ROI. Peripheral outcome will be SDI-PR computed from HR, SC and EMG responses to the index trauma and nightmare scripts. Primary outcome of Exploratory Hypotheses 1A and 1B will be whether or not SDI-PR and HbD are larger in response to trauma-nightmare SDI than to index trauma SDI. Predictor variables for Exploratory Hypothesis 1A will be sleep stage prior to awakening from trauma nightmare. Predictor variables for Exploratory Hypothesis 1B will be ratings by 3 judges, blind to all other participant data, on two 7-point Likert-type scales of 1) the degree of similarity between each individual's index-trauma and trauma-nightmare scripts, and 2) the emotional severity of the recorded trauma-nightmare experience.

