Statistical analyses: As feasibility assessments of NINscan methodology, Hypothesis 1 The gualitative optimization of NINscan's biosensor configuration, biosignal acquisition, event marking, and interface with software delivering SDI stimuli, rather than quantitative hypothesis testing, is the focus of Aim 1. To test Hypothesis 2, the two primary outcome variables (rIFG fNIRS HbD and SDI-PR) will be compared between trauma-nightmare and index-trauma SDI using multiple regression adjusting for age, sex and duration since trauma. Secondary outcome variables (HbD from the 7 remaining fNIRS ROIs) will be compared between groups using the same regression model as for the primary fNIRS outcomes adjusting for multiple comparisons using the false discovery rate. Analysis of Exploratory Hypothesis 1A: We will investigate whether a stronger response to the trauma-nightmare as compared to the indextrauma script is associated with REM sleep using logistic regression, with REM sleep (0/1), sex (M/F) and duration since trauma as predictors. Analysis of Exploratory Hypothesis 1B: The similarity between the trauma-nightmare and index-trauma scripts and the severity of the trauma-nightmare script will be evaluated for each subject by 3 judges using 7-point Likert scales. The relationship between these evaluations and a greater SDI-PR or rIFG HbD response to trauma-nightmare than index-trauma SDI will be assessed using ordinal regression, with sex, judge ID, and duration since trauma as additional covariates.

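### Script order is the only factor the protocol allocates, yet the Exploratory 1A and 1B models omit it. This costs power if an order effect exists and leaves the result exposed to the order split obtained (minor).

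*Combined protocol and SAP*

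**What the plan says.** All references are to the STUDY PROCEDURES section of the combined protocol and SAP.

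- **Allocation.** The overview of the protocol says: "Sessions will be separated by 1 hour and counterbalanced across participants for script order". The Phase 3 paragraph repeats it: "Presentation order of the scripts derived from the TRN and from the index trauma will be counterbalanced across participants". Nothing else in the study is allocated. The text does not say how the order is generated or when it is revealed, or that it is balanced within sleep stage.
- **Outcome.** Under outcome and predictor variables, the exploratory outcome is "whether or not SDI-PR and HbD are larger in response to trauma-nightmare SDI than to index trauma SDI". This is a yes/no result for each person.
- **Models.** The statistical analyses paragraph gives "logistic regression, with REM sleep (0/1), sex (M/F) and duration since trauma as predictors" for 1A and "ordinal regression, with sex, judge ID, and duration since trauma as additional covariates" for 1B. Hypothesis 2 is tested "using multiple regression adjusting for age, sex and duration since trauma". Script order is in none of the three.
- **Power.** For Exploratory Aim 1 the power analysis assumes 50 participants, 60% of nightmares from REM, and response probabilities of 0.70 (REM) and 0.30 (not REM). It claims 80% power with Fisher's exact test at two-tailed 0.05.

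**The concern.** Counterbalancing a factor is a sign that it may matter, and here two related trauma scripts are replayed an hour apart. Suppose responses are weaker in the second session. The nightmare-minus-index difference is then raised in those who hear the nightmare first and lowered in those who hear it second.

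With equal numbers in each order, this cancels from the mean difference tested under Hypothesis 2. It need not cancel in 1A and 1B, which compare people with one another by sleep stage or by judges' ratings. Counterbalancing across the whole sample does not balance order within those subgroups.

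Two things are at stake: unexplained variation that weakens the REM test, and a result that depends on how order happens to fall between REM and non-REM participants.

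**Working it through.** **Plan's own figure.** 50 × 0.60 = 30 REM and 20 non-REM participants. Enumerating Fisher's exact test for Binomial(30, 0.70) against Binomial(20, 0.30) at two-sided 0.05 gives 79.5%, so the stated 80% reproduces.

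**Chance imbalance.** Assume 25 participants per order, assigned independently of sleep stage. Let k be the number of REM participants who hear the nightmare first:

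P(k) = C(30, k) · C(20, 25 − k) / C(50, 25)

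The gap in nightmare-first share is k/30 − (25 − k)/20.

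- Gap of 20 points or more in either direction (k ≥ 18 or k ≤ 12): 14.8%.
- Gap of 30 points or more (k ≥ 19 or k ≤ 11): 4.2%.
- The split 18/30 versus 7/20 is 0.60 − 0.35 = 25 points. The split 19/30 versus 6/20 is 33 points.

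**Order effect (assumed; the documents give none).** The difference score is D = r + s + e, with e ~ N(0, 1).

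- r = ±0.524 for REM/non-REM under the plan's scenario, because Φ(0.524) = 0.70; r = 0 under the null.
- s = +c if the nightmare comes first and −c if second.
- The outcome is 1 when D > 0.

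The two orders therefore differ by 2c. With no REM effect, the probability that the nightmare response is larger is, by order, 0.60/0.40 at c = 0.25, 0.69/0.31 at c = 0.5 and 0.77/0.23 at c = 0.75. REM is tested by a likelihood-ratio test in logistic regression. Sex and duration since trauma are left out for simplicity.

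**Average false-positive rate, order split at random.** About 5-6% with or without the order term, at every c. A second parameterisation, with order odds ratios of 1, 2.25 and 5.44, gives 5.3%, 5.6% and 5.7% without the term and 5.3%, 5.6% and 5.6% with it.

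**Power, planned REM effect, order split at random.**

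| c | Swing 2c (SD) | Without order | With order | Gain (points) |
|---|---|---|---|---|
| 0 | 0 | 84% | 83% | −1 |
| 0.25 | 0.5 | 81% | 82% | 1 |
| 0.5 | 1.0 | 73% | 77% | 4 |
| 0.75 | 1.5 | 61% | 74% | 13 |

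Repeat runs move these entries by up to about 2 points. The cost of omission is the gap within a row. The fall down the columns also reflects holding the REM shift fixed while the order effect grows. The odds-ratio version gives 82.7%, 80.0% and 70.1% without the term against 81.6%, 80.2% and 74.9% with it.

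**False-positive rate given an unlucky split.**

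- 18/30 versus 7/20: about 7% at c = 0.25 and 10% at c = 0.5 without the term; about 5-6% with it.
- 19/30 versus 6/20: about 7% at c = 0.25 and 13% at c = 0.5 without the term; about 6% with it.

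**1B.** No calculation was made. That model is an ordinal regression with three judges' ratings per participant. The argument carries over in structure, since it is also a comparison between people with order left out, but no number is attached to it.

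**The case against.** The strongest reply is that nothing here is bias. If order is independent of sleep stage, chance imbalance is already part of the nominal error rate, and the average rate is not inflated. The conditional figures describe splits that will probably not occur. That stands.

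It is also fair that the order effect is an assumption. A swing of 1.0 to 1.5 SD is about as large as, or larger than, the REM effect the plan hopes to find (2 × 0.524 = 1.05 SD). At a swing of 0.5 SD the gain in power is about 1 point. That stands too, and it limits the severity.

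A reader might go further and infer that an order effect will be reported as a REM, similarity or severity effect. That would require order to track sleep stage or ratings, and nothing in the documents says it does. The 1B ratings are "ratings by 3 judges, blind to all other participant data", so order should not colour them, although blinding does not balance order across ratings.

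A reader might also infer that staff can work out the next order, or that replacing withdrawals upsets the balance. The protocol describes neither alternation nor a visible list. Both sessions fall on one day in Phase 3, after the discharges for too few nightmares and the sleep-disorder exclusions of Phase 1. The text does not say that order is fixed before then.

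What the reply does not remove is that the model leaves out a factor known for every participant, which costs almost nothing to include.

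**Conclusion.** The omission is real and minor. Script order is absent from the 1A and 1B models, and under independent assignment this does not distort the 1A test on average.

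If an order effect exists, omission costs about 1 point of power at a swing of 0.5 SD, 4 points at 1.0 SD and 13 points at 1.5 SD. It also leaves the single result exposed to the order split obtained: there is a 14.8% chance of an imbalance of 20 points or more, and at 18/30 versus 7/20 the error is about 7-10% for c between 0.25 and 0.5.

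These sizes rest on 30 REM and 20 non-REM participants, orders split 25/25, normal difference scores and an assumed c. They apply to 1A only. Hypothesis 2 omits order as well, but with equal orders its mean difference stays unbiased for a simple order effect. Severity is held down because 1A and 1B are labelled exploratory.

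**What to change.** In the statistical analyses paragraph, add script order (nightmare first or index first) as a prespecified covariate in the 1A and 1B models and, for consistency, in the Hypothesis 2 model. Fixing this before analysis also avoids a later, data-driven choice about whether to adjust.

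The cost is one sentence and one degree of freedom, about 1 point of power in 1A if there is no order effect (84% against 83%). No extra participants or procedures are needed.

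As a secondary reporting point, state whether the order is randomly generated, and that it is revealed only after both scripts are final. This would support the independence assumed above.

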In those with posttraumatic stress disorder (PTSD), trauma-related nightmares are a hallmark re-experiencing symptom and a common and severe source of distress often resulting in re-traumatization due to the lack of insight afforded by wakefulness. Proposed research will examine whether such nightmares might serve as targets for imaginal exposure during prolonged exposure therapy (PE), a first line treatment for PTSD. PE produces significant PTSD symptom reduction. However, approximately 30% of patients prematurely drop out from PE treatment and most still meet diagnostic criteria for PTSD at end of treatment. Thus, means for increasing the efficacy of PE are important areas of investigation. Fear extinction learning and memory are the neurocognitive underpinnings of PE. Because increased physiological arousal during PE can aid in extinction learning, recall of trauma-related nightmares might serve as an effective target for PE because of their greater immediacy and salience relative to the more temporally distant traumatic event. Our research group has developed standardized script-driven imagery (SDI) procedures whereby the degree of psychophysiological arousal induced by recollection of the traumatic event that precipitated posttraumatic symptoms (index trauma) can be assessed in those with PTSD. A canonical variable for physiological reactivity to SDI (SDI-PR) is derived from skin conductance (SC), facial electromyography (EMG) and electrocardiography (ECG) and has served as a unitary, objective measure capable of distinguishing those with versus without clinician-diagnosed PTSD. Members of our team have also developed a novel ambulatory device, the NINscan, that can record SC, EMG and ECG along with simultaneous functional near-infrared spectroscopic (fNIRS) imaging of the lateral prefrontal cortex (LPFC). fNIRS yields concentrations of oxygenated ( $O_2Hb$ ) and deoxygenated (HHb) hemoglobin that can be used to assess cortical activation. Specific areas of the LPFC have been shown to activate and/or deactivate during SDI of an index trauma in persons with PTSD. Notably, the LPFC includes the right inferior frontal gyrus (rIFG), a region shown to play a prominent role in inhibiting unwanted behavior and cognition, in which reduced activation accompanies reduced inhibitory performance in persons with PTSD, compared to controls. In participants with PTSD and trauma-related nightmares, proposed research will compare psychophysiological responses and LPFC activation between SDI of a recent trauma-related nightmare versus SDI of the index trauma. During nights over a 2-week period, participants will audio-record timestamped nightmare reports following all nightmare-induced awakenings. During two to four such nights, ambulatory polysomnography (PSG) will allow analysis of sleep physiology immediately preceding nightmare awakenings. A trauma-related nightmare report having sufficient length, clarity and resemblance to the index trauma will be selected and recorded as a script for SDI. The overarching goal of the proposed research will be to compare within-subject similarities and differences in brain and autonomic activation between imaginal replay of a trauma-related nightmare versus imaginal replay of the index trauma to determine the relative degree to which each evokes autonomic and frontocortical activations.

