## Recruitment

The recruitment target is for 50 participants (25 male and 25 female) to complete Phases 1-3 of the study. Withdrawals from the study will be replaced such that the targets for study completers are achieved. We will enroll 2-3 participants/month. Participants will be recruited through: the Boston Medical Center, the VA Boston Healthcare System specialty mental health clinics, the National Center for PTSD participant re-contact database, the Red Sox Foundation and Massachusetts General Hospital Home Base Program, outreach to military or first-responder organizations including our ongoing collaboration with the Boston Fire Department, and outreach to the general public (see below). Key personnel in this study provide access to PTSD patient populations at the above facilities. Specifically, our Consultant, [name]. is an investigator and Clinical Psychologist in the National Center for PTSD and is Assistant Professor in the Department of Psychiatry at Boston University School of Medicine (for which the Boston Medical Center serves as a teaching hospital) and Co-Investigator [name] is Medical Director of the Home Base Outpatient Clinic. Outreach to the general public will occur via internet bulletin boards, social media, MGH research participation websites (e.g., "Rally," "RSVP for health"), e-posting and physical postings at universities, re-contacting participants in past PTSD studies who have signed an agreement to be re-contacted (this is included in our consent forms). Notably, at the VA Boston Healthcare System alone, 6,448 male and 685 female Veterans with a documented PTSD diagnosis attended at least one appointment in FY2017. Based on our consultant [name] previous experiences recruiting participants with PTSD at the VA Boston Healthcare System, we anticipate no difficulty meeting our recruitment goal of 2-3 participants/month.

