**Power analysis:** For the primary outcome in Aim 2, we will compare physiological response and fNIRS in the rLIFC between scripts for the index trauma and the associated nightmare in each of 40 subjects completing the study (i.e., dropouts will be replaced). Based on a paired t-test at the 0.05/2 two-tailed significance level (adjusting for the two outcome measures), we will have 80% power to detect an effect size of d=0.50. In order to power the hypothesis in Exploratory Aim 1, we first assume that each of 50 subjects have one nightmare and that 60% of these nightmares will occur during REM sleep. For this situation, we will have 80% power to detect whether the probability of having greater SDI-PR or rIFG HbD response to the traumanightmare, compared to the index-trauma script is 0.70 or greater for patients who had nightmares during REM sleep, and 0.30 or less for those whose nightmares were not during REM sleep, based on Fisher's exact test, at the 0.05 two-tailed significance level.

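### Exploratory Hypothesis 1B puts three judge ratings per participant into an ordinal regression without handling their correlation; as an ordinary model, its error at a nominal 5% is about 12% at ICC 0.3 and 26-28% at ICC 1

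*Combined protocol and SAP*

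**What the plan says.** In the combined protocol and SAP, the Statistical analyses paragraph says that the similarity of the two scripts and the severity of the nightmare script "will be evaluated for each subject by 3 judges using 7-point Likert scales". The relationship between these ratings and a larger SDI-PR or rIFG HbD response to the nightmare script "will be assessed using ordinal regression, with sex, judge ID, and duration since trauma as additional covariates". That is the whole specification for 1B.

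The paragraph on outcome and predictor variables assigns the roles: "Primary outcome of Exploratory Hypotheses 1A and 1B will be whether or not SDI-PR and HbD are larger in response to trauma-nightmare SDI" than to the index-trauma script, and "Predictor variables for Exploratory Hypothesis 1B will be ratings by 3 judges, blind to all other participant data".

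No significance level, power figure or inter-judge agreement is given for 1B. The nearest stated level is that of the REM comparison in the Power analysis, "based on Fisher's exact test, at the 0.05 two-tailed significance level". On sample size, the Recruitment section says "The recruitment target is for 50 participants". The Power analysis uses 50 for Exploratory Aim 1 and 40 for Aim 2.

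**The concern.** Judge ID differs only between the ratings of one participant. It can enter a model only if the data have one row per judge, hence three rows per participant. On those rows the greater-response indicator is the same, because it has one value per participant, and the ratings are correlated, because all three judges score the same material. Including judge ID adjusts for one judge scoring higher than another. It does nothing about correlation within a participant.

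A model that treats the rows as independent credits the study with more information than it has. Standard errors come out too small, and similarity or severity may be reported as related to nightmare reactivity when it is not.

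A second, separate point is that the two paragraphs disagree on roles. One calls the ratings predictors of a yes/no outcome. The other names ordinal regression, which makes the 7-point rating the dependent variable.

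**Working it through.** The plan states no error rate or power for 1B, so there is no 1B figure to reproduce. As a check on the inputs, the neighbouring power statements were recomputed. Fisher's exact test with 30 versus 20 participants and probabilities 0.70 versus 0.30 gives 79.5%. The paired t-test with 40 participants, d = 0.50 and a two-sided level of 0.025 gives 79.3%. Both agree with the stated 80%.

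**Inputs**
- Ratings per participant: 3 (Statistical analyses).
- Participants: 50 (Recruitment, and the exploratory part of the Power analysis); 40 as an alternative (Aim 2 part of the Power analysis).
- Nominal level: 0.05 two-sided, borrowed from the Fisher test.
- Inter-judge ICC: not in the documents; assumed anywhere from 0 to 1.

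**Rows.** 3 × 50 = 150 per scale (3 × 40 = 120 in the alternative).

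**Formula.** For a factor that is constant within a participant with three rows, the variance is larger than the independence model assumes by 1 + (3 − 1) × ICC = 1 + 2·ICC. The standard error is therefore too small by a factor of about √(1 + 2·ICC), and the actual error is 2 × [1 − Φ(1.96/√(1 + 2·ICC))]. At ICC 0.5 the factor is √2 = 1.41, 1.96/1.414 = 1.386, and the error is 16.6%. The 150 rows then carry the information of 150/2 = 75.

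**Simulation.** Two separately written null simulations fitted a proportional-odds model to three rows per participant, with the response indicator, sex, judge and time since trauma. Simulation A used 2,016 runs per setting and simulation B used 4,000. Results are for the Wald test in B; the likelihood-ratio test in B was within 0.4 points.

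| ICC | SE factor | Formula | A, N=50 | A, N=40 | B, N=50 | B, N=40 |
|---|---|---|---|---|---|---|
| 0 | 1.00 | 5.0% | 6.4% | 6.4% | 5.6% | 4.9% |
| 0.3 | 1.26 | 12.1% | 11.8% | 12.1% | 12.1% | 13.7% |
| 0.5 | 1.41 | 16.6% | 15.9% | 16.5% | 16.8% | not run |
| 0.7 | 1.55 | 20.6% | 21.0% | 21.7% | 22.1% | 21.2% |
| 0.8 | 1.61 | 22.4% | 24.6% | 24.1% | not run | not run |
| 1.0 | 1.73 | 25.8% | 28.3% | 28.3% | 27.6% | 27.5% |

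In B at N=50, uneven rating categories gave 5.6/11.8/20.6/28.8% at ICC 0/0.3/0.7/1, and 70% responders gave 5.5/12.4/21.4/27.6%. The simulated ICC is on the latent scale. On the observed 7-point scores, 0.3 corresponds to about 0.27 and 0.7 to about 0.65.

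**Swapping the roles.** Logistic regression of the yes/no response on single ratings, still with three rows, gave 15.4% at ICC 0.5 and 20.5% at 0.7 (A, N=50). The role question therefore does not decide the matter.

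**Repairs, tested under the same null**
- Logistic regression on the averaged rating, one row per participant: 4.2-5.5% at N=50 and 4.3-5.2% at N=40 (A).
- Ordinal model with participant-clustered standard errors: 4.4-6.2% at N=50 and 4.9-7.2% at N=40 (A); 4.7-6.6% over all settings (B).
- Ordinal model with a participant random intercept: checked at one setting only (N=50, ICC 0.3) in a short run, 4.5% against 12.3% for the ordinary model.

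**The case against.** The best counter-argument is that this is an omission and not a stated error. The Statistical analyses paragraph names every model only by family. Hypothesis 2 is called just multiple regression, yet the Power analysis shows that the authors regard those data as paired. Naming judge ID suggests that they had the multi-rater structure in mind, and ordinal regression does not exclude a mixed or clustered version. It is fair that the error rates apply only if an ordinary ordinal model is fitted. However, the plan lists its covariates explicitly and the participant is not among them, so an analyst following it literally would fit independent rows.

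Other points stand in part:
- **Size.** It is undetermined without an ICC. Scripts are chosen for "having sufficient length, clarity and resemblance to the index trauma will be selected", which may narrow the spread of true similarity and lower the ICC on that scale. Inflation is absent only near ICC 0, though, where the ratings would be of no use as a measure.
- **Information.** Below ICC 1 the second and third ratings do add some, so participants are not simply counted three times.
- **Formula.** The square-root factor is an approximation; at ICC 0.8 and above the simulations run about 2 to 3 points higher.
- **N=40.** This figure belongs to Aim 2, so 50 is the main case.
- **Number of tests.** Two ratings by two responses make four tests if each rating is modelled separately. If both ratings enter one model as predictors, there are two models.
- **Consequence.** 1B is exploratory and carries no power claim. That limits the harm but does not make its p-values correct.

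**Conclusion.** The concern holds. The stated model and covariates require three correlated rows per participant, and nothing in the plan accounts for the correlation. Fitted as an ordinary ordinal regression, each 1B test at a nominal two-sided 5% has an actual error of about 5-6% at ICC 0, 12% at 0.3, 21% at 0.7 and 26-28% at 1. Formula and simulations agree to within about 3 points throughout.

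This rests on three assumptions: independent-row fitting, the borrowed 5% level, and an ICC that the documents do not give. The effect is confined to Exploratory Hypothesis 1B. Hypothesis 2, the recruitment target and the stated power figures are untouched. The predictor/outcome mismatch is a real inconsistency to be reconciled, but the inflation is nearly the same under either reading. The change should be made before analysis.

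**What to change.** Keep the pre-specified yes/no greater-response variable and write one of these into the Statistical analyses paragraph:

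- **(a)** Average the three judges' ratings into one similarity score and one severity score per participant. Use each as a predictor in a logistic regression of the yes/no response with sex and time since trauma, one row per participant and no judge term. This fits the roles in the outcome and predictor paragraph and the logistic model already planned for 1A. It gives up the estimate of differences between judges.
- **(b)** Keep the ordinal model on single ratings with judge ID, and add participant-clustered standard errors or a participant random intercept. Then correct the predictor and outcome labels in the outcome and predictor paragraph. Clustered standard errors can be slightly liberal in a sample this small.

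Under either option, report the inter-judge ICC for both scales, state the significance level for 1B, and say how many tests it comprises.

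The cost is analysis wording only, with no new data, visits or participants. Results may look less significant, because precision that was never there is removed.
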